#### **7.4.2 Screening**

The TVT member will complete a log of all patients screened for eligibility who are not registered either because they are ineligible or because they declined participation. All anonymised screening logs will be returned to the CTRU.

Anonymised information will be collected including:

- The reason not eligible for study participation or
- Eligible but declined
- Date of Birth
- Gender
- Ethnicity
- Pressure ulcer grade and location

### **7.5 Data collection/assessment**

Study data will be recorded by members of the TVTs or the researcher on the case record forms (CRFs) and by patients, members of the TVTs or the researcher on questionnaire booklets. Anonymised data will be returned to the CTRU.

Assessments will be undertaken as follows:

- Registration and Baseline data
- PU-QOL Questionnaire booklet

#### **7.5.1 Registration and Baseline Data**

Patients who meet the inclusion criteria and provide informed written consent (for baseline assessment and questionnaire completion) will be registered to this study. Registration and baseline information will be recorded by the TVT member or researcher including:

- Patient initials and date of birth
- Gender
- Ethnicity
- Marital status
- Education
- Presence of PU symptoms
- Pressure ulcer grade, location and number of pressure ulcers
- Duration of pressure ulcer
- Treatment plan (information about which treatment interventions the patient is currently receiving)
- Co-morbidity and/or speciality (i.e. spinal cord injured, trauma, vascular, care of the elderly ward)
- Centre code
- Name of the TVT/clinical research staff member conducting registration
- Confirmation of eligibility and written informed consent
- Braden scale

### **7.5.2 PU-QOL questionnaire booklet**

#### **Self-complete version**

The patients will self-complete the PU-QOL questionnaire booklet, which will be provided to them by the person obtaining consent (i.e. member of the TVT or the researcher (CG)). It is anticipated that completion of the questionnaire may take up to 40 minutes.

#### **Interview-administered version**

A questionnaire pack will be administered to patients by either a member of the TVT or the researcher, following an interview manual. It is anticipated that administration of the questionnaire may take up to 40 minutes. Training in administering the questionnaire will be provided by the CTRU.

### **7.6 Item reduction analysis**

The purpose of the item reduction analysis is to produce a psychometrically robust short version of the PU-QOL questionnaire. Standard psychometric tests and criteria for acceptability, reliability and validity will be performed to identify and retain items with strong psychometric properties and eliminate items with poor psychometric properties to produce a shorter, item-reduced version of the PU-QOL questionnaire. These analyses will also evaluate the hypothesised subscales of the questionnaire

Item reduction analysis will include item analysis and principal component factor analyses, including missing data <5%, maximum endorsement frequencies <80% (floor/ceiling effects <80%), aggregate adjacent endorsement frequencies >10%, item redundancy (inter-item correlations <0.75), internal consistency (item-total correlations <0.25), evidence of item responsiveness, and tests of scaling assumptions (item convergent/discriminant validity). A preliminary psychometric evaluation of the short, item-reduced version will be carried out using standard psychometric tests for acceptability, reliability (internal consistency), and validity (factor analysis, item convergent/discriminant validity).

In addition to standard psychometric tests, methods from modern measurement theory will be used to evaluate the psychometric properties of the PU-QOL questionnaires' scales and items [36]. This is proposed in order to strengthen methodological rigour.

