## **7.3 Methods**

An approximate sample of 150-250 PU patients will be purposively sampled ensuring representation of patients with all PU categories (grades 1-4, Table 1) and treatment types. There are no formal sample size estimation methods for evaluation of PRO measures, so the 'rule of thumb' recommendation of 5-10 patients for every item in the questionnaire has been used to estimate the sample size of 150-250 patients [24]. Consecutive patients will be identified and approached to participate. Accrual will be reviewed to ensure that there is balanced representation of patients in all PU categories. If we are validating the questionnaire for both modes of administration (i.e. self-complete and interview-administered modes) then accrual will be monitored to ensure equal numbers of patients are recruited into both mode groups. Where possible patient recruitment will be piggy-backed onto local audit and Quality Assurance (QA) activity (prevalence surveys, incidence monitoring, critical

incidence reporting) to maximise the identification of patients with PUs whilst minimising disruption and demand on the local clinical team.

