### **8.6 Psychometric evaluation analysis**

Analyses will include examination of:

**Item-level performance** will determine missing data (<5%), maximum endorsement frequencies (<80%), and item redundancy (inter-item correlations <0.75).

**Acceptability** will be assessed by completeness of data (e.g. missing data for summary scores <5%) and score distributions (e.g. distribution of endorsement frequencies across response categories, skew and floor/ceiling effects for summary scores <10%).

**Reliability** will be assessed on the basis of internal consistency (Cronbach's alpha for summary scores  $\geq 0.70$  and item-total correlations  $\geq 0.30$ ) and test-retest reliability (correlations for summary scores  $\geq 0.70$ ).

**Validity** will include a within-scale analyses to determine whether a single entity (construct) is being measured and that items on the measure can be combined to form a summary score (Cronbach's alpha  $\geq 0.70$ ), and analysis against external criteria (convergent, discriminant and known groups differences validity). To evaluate convergent validity we will compare PU-QOL with the SF-12, and additional relevant measures as determined once the PU-QOL questionnaire is developed. Discriminant validity will be assessed by examining PU-QOL scores by age, gender and medical specialty. PU-QOL scores for patients by PU severity (superficial vs severe), site of PU (heel vs elsewhere), and sensitivity impaired vs. no sensitivity impaired will be compared to evaluate known group differences. Factor analysis, together with the results of other item-level analyses described in table 2, will be used to investigate hypothesised subscales.

**Evaluation of subscales** will be determined by factor analysis and item convergent/discriminant validity

In addition to standard psychometric tests, modern psychometric methods will be used to strengthen methodological rigour [36].

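### In section 7.6 the item-total criterion (<0.25) points the opposite way from every other numeric limit in its list and from section 8.6 (≥0.30), so the rule has no consistent reading as written

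*Protocol*

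**What the plan says.** Protocol section 7.6 sets the purpose of the field test 1 item analysis: to "identify and retain items with strong psychometric properties and eliminate items with poor psychometric properties". The next paragraph gives the criteria in one continuous list, with no label saying whether a value means keep or drop:

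- The first entries cover completeness and spread of responses, as percentages: "missing data <5%, maximum endorsement frequencies <80% (floor/ceiling effects <80".
- The next concerns use of neighbouring response categories, again as a percentage: "aggregate adjacent endorsement frequencies >10".
- Overlap between pairs of items is limited by this entry: "item redundancy (inter-item correlations <0.75".
- Coherence of an item with its scale comes last among the numeric limits: "internal consistency (item-total correlations <0.25".

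Two further entries, one on responsiveness and one on scaling, carry no numeric limit.

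Section 8.6, for field test 2, repeats the missing-data, maximum-endorsement and inter-item limits with the same values and direction. Under reliability it gives the item-total limit as "item-total correlations $\geq 0.30"$, beside a Cronbach's alpha of at least 0.70 for summary scores. The protocol gives no reason for the opposite sign in 7.6 or for the change from 0.25 to 0.30.

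**The concern.** A list of thresholds is usable only if the reader knows which side of each threshold is good. In 7.6, four of the five criteria give the good side and the fifth gives the bad side. An analyst who codes the list uniformly as conditions for keeping an item would reverse the internal-consistency screen: weakly related items would pass and items that hold the scale together would be flagged. The item-reduced questionnaire is the main product of field test 1 and is what field test 2 evaluates, so the rule that produces it should not need correcting from outside knowledge.

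The two stages also use different cut-offs, 0.25 and 0.30. This is a secondary matter. It affects only items in a narrow band and has no part in the reversal.

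**Working it through.** The 0.25 is a stated threshold, not a derived figure, so there is no calculation of the plan's to reproduce. The check is mainly one of logic.

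**1. Direction of each limit**

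| Criterion | 7.6 | 8.6 | An item meeting the 7.6 value is |
|---|---|---|---|
| Missing data | <5% | <5% | acceptable |
| Maximum endorsement | <80% | <80% | acceptable |
| Adjacent endorsement | >10% | not listed | acceptable |
| Inter-item correlation | <0.75 | <0.75 | acceptable (not redundant) |
| Item-total correlation | <0.25 | ≥0.30 | poor |

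**2. Can one reading serve the whole list?**

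- All retention limits: four entries work. The item-total entry keeps weak items and drops strong ones.
- All elimination limits: the item-total entry works. The other four would remove items with little missing data, well-spread responses and no redundancy.

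Neither uniform reading serves the stated purpose. Only a mixed reading does, and the text does not announce one.

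**3. Example items under each version of the rule**

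| Item-total r | 7.6 literal (keep if <0.25) | 7.6 sign reversed (keep if ≥0.25) | 8.6 (pass if ≥0.30) |
|---|---|---|---|
| 0.10 | keep | drop | fail |
| 0.24 | keep | drop | fail |
| 0.27 | drop | keep | fail |
| 0.30 | drop | keep | pass |
| 0.50 | drop | keep | pass |
| 0.70 | drop | keep | pass |

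The sets r < 0.25 and r ≥ 0.30 do not overlap, so at the same correlation nothing kept by the literal rule passes 8.6. Reversing the sign restores sensible selection. What then remains is the band from 0.25 to below 0.30.

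**4. How far the literal rule would fall short (illustration)**

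Assume k parallel items, which the protocol does not state. With mean inter-item correlation r, the corrected item-total correlation is c = r√(k−1) / √(1+(k−2)r), and alpha = kr / (1+(k−1)r). Put every item at the ceiling, c = 0.25, and solve for r:

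| k | r | alpha |
|---|---|---|
| 3 | 0.193 | 0.42 |
| 5 | 0.151 | 0.47 |
| 10 | 0.116 | 0.57 |
| 20 | 0.094 | 0.68 |
| 24 | 0.090 | 0.70 |

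For k = 10, for example, alpha = 10 × 0.116 / (1 + 9 × 0.116) = 1.16 / 2.044 = 0.57. A scale built by the literal rule would miss the alpha of 0.70 in 8.6 unless it had about 24 items or more.

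**5. The 0.25 to 0.30 band**

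Take a true correlation of 0.27, unchanged between the two versions, and the field test 2 sample of 150 to 250 (section 8.3). By Fisher's z, atanh(0.30) − atanh(0.27) = 0.3095 − 0.2769 = 0.0327.

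- n = 150: 0.0327 × √147 = 0.40, so the chance of observing at least 0.30 is about 35%.
- n = 250: 0.0327 × √247 = 0.51, so the chance is about 30%.

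Such an item would more often miss the 8.6 limit than meet it, but failure is far from certain.

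**The case against.** The strongest reply is that no competent analyst would apply the entry literally. The list has no keep-if label, the preceding sentence says poor items are to be eliminated, and the entry is headed internal consistency, where a low value can only be bad. The entry is therefore naturally read as a flag. This stands as to likely intent. It does not make the text right, because the reader must know which entry to turn round.

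There are also safeguards. Sections 5.1, 7 and 7.1 treat poorly performing items as candidates for removal, so failing one criterion does not remove an item automatically. The item-total value sits beside factor analysis, item convergent/discriminant validity and modern measurement methods. Section 7.6 also re-examines the internal consistency of the reduced version within field test 1, where the alphas in the illustration would expose a reversed selection. This stands too, and it limits the practical risk.

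A reader might infer that the study will keep the wrong items. The documents do not support that: it follows only from literal application, which the stated purpose argues against.

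A reader might also take 0.25 against 0.30 as a contradiction. It need not be one. Section 7.6 screens the long version and 8.6 evaluates the shortened one. The total differs between them, and a looser screen before a stricter evaluation can be deliberate. Nor does 8.6 attach item removal or failure of the instrument to one item falling below 0.30.

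**Conclusion.** The point holds as a directional error in a stated threshold. In 7.6 the item-total limit runs against every other numeric limit in its list and against 8.6, and neither uniform reading of the list works. This rests on the text alone.

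The size of the consequence is conditional. Under literal application, selection on this criterion is fully reversed and shares no correlation value with the 8.6 limit. Under the probable intent of an elimination flag below 0.25, selection is sound and the fault is one of clarity. The alpha figures assume parallel items and illustrate only the literal case.

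The difference between 0.25 and 0.30 is secondary. It concerns only items from 0.25 to below 0.30, does not cause wrong selection, and needs either alignment or a sentence of explanation. The stronger inference that such items are bound to fail field test 2 is not supported, given the chance of about 30% to 35% of reaching 0.30 when the true value is 0.27 and is unchanged between versions.

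**What to change.** In section 7.6, state that all the listed values are retention limits, and reverse the sign so that the entry reads *item-total correlations ≥0.25*. Then do one of two things: raise the value to 0.30 to match section 8.6, or add a sentence saying that 0.25 is a deliberately looser screen on the long version. The documents do not settle which of these is preferable.

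The cost is a line or two of text, with no effect on recruitment or data collection. If the cut-off is aligned at 0.30, an item or two between 0.25 and 0.30 may be dropped earlier. If 0.25 is kept, the sponsor accepts that some retained items may fall short of the 8.6 limit in field test 2.

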## **8 FIELD TEST 2: PSYCHOMETRIC EVALUATION**

### **8.1 Design for field test 2**

In order to establish the PU-QOL as a valid measure of PU HRQL and to determine whether the instrument meets gold-standard criteria, scientific psychometric tests of acceptability, reliability, and validity will be performed.

A questionnaire pack will be provided to patients to self-complete or be administered to them. The pack will include the PU-QOL instrument and additional measures selected for validation purposes (section 8.5.1). In addition, a sub-sample of the patients who complete and return the questionnaire packs at baseline will be asked to self-complete or have administered to them a second (re-test) questionnaire pack 2-7 days after the initial questionnaire completion.

## **8.2 Eligibility**

Patients from participating acute and community trusts, with existing PUs (any grade, see Table 1), will be included in the study if they are hospital in-patients or hospital outpatient, or intermediate out-patient, nursing home patients or community patients under the care of community care nursing services, and they fulfil the criteria detailed in section 7.2.

## **8.3 Methods**

An approximate sample of 150-250 PU patients (5-10 patients for each item on the PU-QOL instrument) will be purposively sampled ensuring representation of patients with all PU categories (grades 1-4, Table 1) and treatment types. Consecutive patients will be identified and approached to participate. Accrual will be reviewed to ensure that there is balanced representation of patients in all PU categories. If we are validating the questionnaire for both modes of administration (i.e. self-complete and interview-administered modes) then accrual will be monitored to ensure equal numbers of patients are recruited into both mode groups. Where possible, patient recruitment will be piggy-backed onto local audit and QA activity (prevalence surveys, incidence monitoring, critical incidence reporting) to maximise the identification of patients with PUs by the local clinical team.

### **Test-Retest**

A test-retest will be undertaken with a sub-sample of participants recruited for the final field test. Consenting participants will complete a second questionnaire pack 2-7 days after the first questionnaire pack (approximately 75 patients for each mode of administration group). The length of the test-retest interval must be short enough to ensure that clinical change in the PU is unlikely to occur, but sufficiently long to ensure that respondents do not recall their responses from the first assessment. A short test-retest interval is necessary to ensure that stability per se is being evaluated, rather than clinical change in the PU during the test-retest interval, which will underestimate reliability.

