## **8.5 Data collection/assessments**

Study data will be recorded by members of the TVTs on the CRFs and by patients on questionnaire packs. Data will be returned to the CTRU.

Assessments will be undertaken as follows:

- Registration and Baseline
- PU-QOL Questionnaire booklet

- 2-7 day follow-up questionnaire pack (approx. 75 patients from baseline sample)

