### **8.5.2 PU-QOL questionnaire pack**

Baseline questionnaire pack will include:

- The Provisional PU-QOL
- SF-12 (rather than SF36 to reduce respondent burden)
- Additional questionnaires selected for validation purposes (ethics will be notified about which questionnaires are selected, section 8.5.3)

Test-retest questionnaire pack will include:

- The Provisional PU-QOL
- SF-12 (rather than SF36 to reduce respondent burden)
- Additional questionnaires selected for validation purposes (ethics will be notified about which questionnaires are selected, section 8.5.3)

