## **12 ETHICAL CONSIDERATIONS**

This project will recruit patients with PUs and therefore will include elderly and highly dependent patients considered as vulnerable. Ethical issues are largely related to the involvement of vulnerable adults/elderly patients with high levels of co-morbidity including acute and chronic illness. Clinically, older patients are treated in the same way as younger patients and it is therefore important to ensure that the study is representative of the clinical population. In addition, questionnaire completion/interview requires the patient to reflect on their experience of having a PU and how interventions received have impacted on their QOL. For some people this may raise topics considered to be sensitive, embarrassing or upsetting, and possibly emotionally distressing.

The ethical issues surrounding these potentially vulnerable patients have been addressed through the study design and include a thought out consent process, the use of one-to-one

semi-structured interviews using de-briefing questioning for data collection at the development pre-testing stage to provide a caring and supportive environment in which to discuss any sensitive issues that may arise, and the use of only essential measures required for validation purposes (short version where available) to reduce respondent burden. If the patient becomes distressed during the interview or from completing the questionnaire, then the interview will be immediately stopped. It will be stressed to all patients that they are able to withdraw from participation at any time without giving reason, and without any effect on their care. They will be referred back to their treating nurse specialist if required.

This study will be conducted in accordance with the Declaration of Helsinki in its latest form. The study will be submitted to and approved by a REC prior to identifying eligible patients. The CTRU will provide the REC with a copy of the final protocol, patient information leaflets, consent forms, and all other relevant study documentation.

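### Nothing recorded at retest shows whether the ulcer changed, so a correlation below 0.70 could not be attributed to the scale rather than to clinical change

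*Protocol*

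**What the plan says.** Protocol section 8.3 (Test-Retest) plans a second questionnaire 2-7 days after the first in a sub-sample of field test 2. It names the threat: the aim is to measure stability "rather than clinical change in the PU during the test-retest interval, which will underestimate reliability". It also names the control: "The length of the test-retest interval must be short enough to ensure that clinical change in the PU is unlikely to occur".

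The other relevant sections are:

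- **8.5** lists one assessment after baseline: "2-7 day follow-up questionnaire pack (approx. 75 patients from baseline sample").
- **8.5.1** has ulcer grade, location, number, duration and symptoms recorded under registration and baseline data. No retest counterpart is listed.
- **8.5.2** ("Test-retest questionnaire pack will include") gives the retest pack the same three entries as the baseline pack: the PU-QOL, the SF-12 and further questionnaires chosen for validation.
- **8.4** (Self-complete version) allows the second booklet to be handed over when the first is collected, or to be posted. For a patient at home, no staff member need see the ulcer at retest.
- **8.6** gives the criterion, "test-retest reliability (correlations for summary scores" at least 0.70). It states neither the type of correlation nor any stable-patient subset.

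**The concern.** A test-retest correlation estimates reliability only in patients whose true state stayed the same. Where true scores move by different amounts in different patients, that movement enters the correlation as if it were measurement error. The protocol recognises this but collects nothing that would show in whom it happened.

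What is at stake is the interpretation of the 0.70 criterion. If a summary score falls below it, the sponsor could not tell an unreliable scale from a reliable scale applied to patients whose ulcers changed. Field test 2 enrols all grades, from intact-skin erythema to extensive tissue destruction, and settings from acute wards to the community (8.2, 8.3, Table 1), so stability may well differ between patients. This is a gap in data collection. An analysis plan can define a stable subset only if stability was recorded.

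**Working it through.** **Plan's own figures.** The protocol derives neither the 75 retests nor the 0.70 limit, so there is nothing to reproduce.

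**Inputs from the protocol**
- Limit 0.70 (8.6) and interval 2-7 days (8.3).
- n = 75 pairs per correlation. Section 8.3 gives about 75 for each mode group, while 8.5 gives about 75 from the baseline sample. I use 75.

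**Assumed inputs (not in the documents)**
- R, the retest correlation in stable patients: 0.75 or 0.80, with 0.85 and 0.90 for context.
- p, the share of patients whose true score changes: 10, 20 or 30%.
- Change among those patients: mean m = 0.8 and SD s = 0.4 in baseline-SD units, independent of the baseline score.

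**Step 1: expected correlation.** With first score T + e1 and second score T + D + e2 (baseline variance 1, T having variance R), the variance of D over all retested patients is

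V = p(s² + m²) − (pm)², and expected r = R / √(1 + V).

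Here s² + m² = 0.16 + 0.64 = 0.80.

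| p | V | √(1+V) | r, R = 0.75 | r, R = 0.80 |
|---|---|---|---|---|
| 10% | 0.080 − 0.0064 = 0.0736 | 1.036 | 0.72 | 0.77 |
| 20% | 0.160 − 0.0256 = 0.1344 | 1.065 | 0.70 | 0.75 |
| 30% | 0.240 − 0.0576 = 0.1824 | 1.087 | 0.69 | 0.74 |

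**Step 2: other assumptions about change.** With 20% changing and R = 0.75, a uniform 0.5 SD change in those patients (m = 0.5, s = 0) gives r = 0.735. Change in both directions with SD 1.0 (m = 0, s = 1.0) gives 0.685. The same two cases at R = 0.80 give 0.784 and 0.730. An identical shift in every patient gives V = 0 and leaves a Pearson correlation unchanged.

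**Step 3: how much change reaches the limit.** Setting r = 0.70 gives √V = √((R/0.70)² − 1), the SD of true change over all retested patients. It is 0.38 baseline SDs at R = 0.75, 0.55 at 0.80, 0.69 at 0.85 and 0.81 at 0.90. For comparison, √V in Step 1 is 0.27, 0.37 and 0.43.

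**Step 4: chance of meeting 0.70 with 75 pairs.** By Fisher's z, this is Φ[(atanh r − atanh 0.70)·√72].

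| | no change | 10% | 20% | 30% |
|---|---|---|---|---|
| R = 0.75 | 82% | 66% | 53% | 43% |
| R = 0.80 | 97.5% | 91% | 82% | 73% |

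**Step 5: precision and the price of a stable subset.** The 95% interval is tanh(atanh r ± 1.96/√(n − 3)). At r = 0.75 with 75 pairs it is 0.630 to 0.835. If 20% are set aside, 0.8 × 75 = 60 pairs remain and it is 0.613 to 0.843.

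**The case against.** The best defence is that the protocol names a risk and adopts a reasonable control. A 2-7 day interval is a real safeguard, and if it works there is little change to detect. No section gives a rate of ulcer change by grade or setting, and an ulcer that changes need not move a quality-of-life summary score by 0.8 SD. In Step 1 the loss at 20% changing is about 0.05, smaller than the sampling uncertainty with 75 pairs. At true reliability 0.80 the expected correlation stays above 0.70 even with 30% changing. All of this stands. It limits the size of the point, but it does not supply the missing information: a short interval makes change less likely without showing who changed.

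A reader might infer that the protocol contradicts itself, or that its reliability estimate is bound to be too low. The text supports neither. The bias arises only if true scores change, and differ between patients, within the interval.

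A reader might also infer that repeating the SF-12 and other measures breaks the ethics section's commitment to "the use of only essential measures required for validation purposes". That goes too far. The commitment concerns which measures are chosen and the use of short versions, and does not promise a shorter retest pack. An analysis plan not seen here may use the repeated SF-12, and an identical pack keeps administration conditions the same. However, the SF-12 is generic and cannot show whether the ulcer changed.

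**Conclusion.** The point holds as a gap in data collection with an inexpensive remedy. The protocol identifies a downward bias, relies on the interval alone to prevent it, and records nothing at retest that would show whether it occurred.

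The size is unknown from the documents. Under the assumed change pattern, the expected correlation falls by 0.03 to 0.06. That can decide the result at true reliability 0.75, where the chance of meeting 0.70 drops from 82% to 43% with 30% changing. It matters less at 0.80, and at 0.90 it would take a true-change SD of 0.81 over all patients to bring the expected correlation down to the limit. These figures assume a Pearson correlation, change independent of baseline score, and the stated share and size of change.

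**What to change.** In 8.5.2, add one question to the retest pack: whether the pressure ulcer is better, the same or worse since the first questionnaire. It works equally in posted, handed-over and interviewer-administered packs.

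In 8.6, judge the 0.70 limit in patients answering 'same', and report the all-pairs correlation alongside.

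The cost is one item, fewer pairs and a somewhat wider interval in the stable-patient estimate (Step 5). The subset also relies on patients' own rating of change, which will misclassify some of them. Reporting both results lets a reader see how far the conclusion depends on that rating.

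As a secondary point, the sponsor may wish to confirm that the SF-12 and the additional measures are needed at retest, since 8.6 names no retest use for them.
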